### **15.4 Analysis of Secondary Endpoints**

Logistic regression will be used to assess the association of spironolactone with each dichotomous outcome, and ordinal logistic or linear regression used to evaluate the association of spironolactone with change in either ordered categories or continuous measures, where appropriate.

Safety and tolerability data will be summarized by treatment group.

Adverse event rates will be coded by body system and MedDRA classification term. Adverse events will be tabulated by treatment group and will include the number of patients for whom the event occurred, the rate of occurrence, and the severity and relationship to study drug.

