NUMBER OF SUBJECTS	30 total women: 20 randomized to spironolactone and 10 randomized to placebo
SUBJECT SELECTION CRITERIA	
Key Inclusion Criteria:
 
 
- Women with NASH identified on standard of care liver biopsy performed for clinical purposes.
 
 
Key Exclusion Criteria:
 
 
- Uncontrolled diabetes
 
- Alcohol consumption >2 drinks per day for at least 3 consecutive months over the previous 5 years
 
- Other chronic liver disease (i.e. hepatitis B virus, hepatitis C virus, autoimmune hepatitis) or cirrhosis from any cause
 
- Recent or planned upcoming weight reduction surgery within five years of diagnosis of biopsy-confirmed NASH
 
- HIV infection
 
- Drugs associated with fatty liver (i.e. amiodarone, methotrexate, systemic glucocorticoids, tamoxifen, anabolic steroids, valproic acid) for more than 4 weeks prior to baseline or during study
 
- Recent, current, or planned upcoming pregnancy or current perimenopausal status
 
- Renal impairment (glomerular filtration rate <45 ml/min/1.73m or potassium levels > 5.0 mmol/L)
 
- Androgen receptor antagonist use (i.e. flutamide, spironolactone or flutamide) for more than 3 months within one year prior to baseline
 

TEST PRODUCT, DOSE, AND ROUTE OF ADMINISTRATION	Spironolactone 100mg. Product will be administered orally once daily for a length of 6 to 12 months.
CONTROL PRODUCT, DOSE AND ROUTE OF ADMINISTRATION	Placebo. Product will be administered orally once daily for a length of 6 months.
DURATION OF SUBJECT PARTICIPATION AND DURATION OF STUDY	
Subjects will be on study for up to 10 or 16 months
 
Screening: up to one month
 
Treatment: 6 to 12 months
 
Follow-up: up to 3 months from end of treatment
 
The total duration of the study is expected to be 4 years. Women will be enrolled and treated on a rolling basis, with a 30 month total recruitment period, 6 to 12 months of treatment per participant, and up to 3 months for the final subject follow-up post treatment.

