CONCOMMITANT MEDICATIONS- PROHIBITED	
 
- Androgen receptor antagonists (i.e. flutamide or flutamide) including current use of spironolactone
 
- Eplerenone as also blocks aldosterone receptor
 
- Drugs associated with fatty liver (i.e. amiodarone, methotrexate, systemic glucocorticoids, tamoxifen, anabolic steroids, valproic acid)
 

EFFICACY EVALUATIONS	
As a pilot trial this study is not powered to detect an effect of spironolactone on NASH progression in women. The primary goal of the study is rather to evaluate the feasibility and tolerability of the study intervention and outcome measures in women with NASH while also exploring the mechanisms by which blocking testosterone receptors may alter NASH severity or associated metabolic comorbidities leading to NASH. If the intervention is deemed to be feasible, and we detect a signal that spironolactone may alter these biologic processes, then these data would be used to support a larger trial aimed at assessing the efficacy of spironolactone or other related androgen modulating medication on the treatment of NASH in women.

PRIMARY ENDPOINTS	
Feasibility endpoints:
 
 
• Adherence and acceptability of spironolactone in women with NASH
 
• Adherence and acceptability of study outcome measures (MRI and optional EOT biopsy)
 
 
Determine the range of NASH on baseline biopsy to inform inclusion criteria for larger trials

SECONDARY ENDPOINTS	
 
• Biochemical endpoints: serum lipids, HOMA-IR, liver enzymes
 
• Radiologic endpoints: liver fat quantity, visceral fat volume, liver inflammation, liver scarring
 
• Histologic endpoints: Change in NAFLD Activity Score (NAS)
 
• Expression of androgen receptors in the liver and circulating hormone levels.
 

SAFETY EVALUATIONS	
Spironolactone is an old, commonly used medication to treat symptoms of high androgens in women therefore has a longstanding favorable side effect profile. Change in clinical safety labs and in person review of potential side effects will be assessed at each study visit. Incidence of adverse events will be collected.

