### 5.2 Secondary Endpoints

- Biochemical endpoints: serum lipids, HOMA-IR, liver enzymes. These endpoints will be examined because existing data outside of NASH suggest that androgen blockade may alter these metabolic pathways. These metabolic pathways are also keys players in the development and progression of NASH, therefore understanding the biologic mechanism of androgen blockade in women with NASH could be used to support the need for a larger clinical trial aimed at evaluating such hormone modulation to treat NASH in women.
- Histologic endpoints- Change in the NAFLD activity score (NAS), which measures different components of NASH on liver biopsy. If we detect a signal that spironolactone may affect NASH histology, these data could also help support need for larger trial evaluating efficacy of androgen modulating therapy for treatment of NASH in women.
- Expression of androgen receptors in the liver and circulating hormone levels. It is not known whether spironolactone changes expression of androgen receptors in the liver, and this research question can help us to understand the mechanism of spironolactone effects on the liver. Likewise, data are conflicting on whether spironolactone changes circulating hormone levels, and this pathway will be studied by measuring hormone levels pre and post treatment.

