### **15.6 Sample Size and Randomization**

The sample size of 30 with 2:1 randomization was determined based on budget and feasibility within a 4-year grant timeline. The sample size is also reasonable for pilot trial, and will allow us to estimate effects and feasibility with reasonable precision. The 2:1 randomization was selected to increase the chance that women would receive the treatment, and therefore potentially increase study enrollment, while still allowing the investigator to obtain the necessary training in conducting a placebo-controlled trial in preparation for a larger trial in the future, and allowing for preliminary endpoint assessments in the treatment as compared to placebo groups.

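### Section 15.4 names neither an outcome scale nor a baseline covariate for the continuous secondary endpoints; if the markers are right-skewed, regressing untransformed change in 20 vs 10 women gives up precision that costs only wording to recover

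*Combined protocol and SAP*

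**What the plan says.** Section 15.4 is the only text that gives a model for the continuous measures: "ordinal logistic or linear regression used to evaluate the association of spironolactone with change in either ordered categories or continuous measures", with a closing qualifier that limits this to where it is fitting. No section names a transformation, the outcome's baseline value as a covariate, a variance estimator, or a rank or permutation alternative. The synopsis allows adjustment only for variables that turn out clearly unbalanced between the arms.

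The measures concerned are set out in Section 5.2. One group is listed as "Biochemical endpoints: serum lipids, HOMA-IR, liver enzymes"; for the hormones, "this pathway will be studied by measuring hormone levels pre and post treatment". Triglycerides are not named, but Section 9.2.1 includes a lipid panel. Liver fat is a radiologic endpoint, placed under secondary endpoints in the synopsis and under primary endpoints in Section 5.1. Either way, Section 15.4 gives the only model that fits it, because Section 15.3 covers only rates.

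The synopsis gives the size as "30 total women: 20 randomized to spironolactone and 10 randomized to placebo". Section 15.6 bases this on budget and feasibility and says that it "will allow us to estimate effects and feasibility with reasonable precision". The synopsis also states: "As a pilot trial this study is not powered to detect an effect of spironolactone on NASH progression in women". The opening of Section 15 promises a detailed SAP before the final analysis, which may modify these methods.

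**The concern.** The plainest reading of Section 15.4 is follow-up minus baseline in original units, regressed on arm. HOMA-IR is a product of glucose and insulin, and enzymes, triglycerides and hormones are positive concentrations. Measures of this kind are often right-skewed. If they are skewed here, the few women with the highest baselines produce most of the variance of untransformed change, and they blur the contrast for everyone else.

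A simple change score also uses the baseline inefficiently, on either scale. It subtracts the whole baseline value, whereas covariate adjustment removes only the part that predicts follow-up.

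At stake is the second purpose of the pilot. The synopsis and Section 2 say that a signal on these biological measures would support a larger trial. With 20 vs 10 women there is little precision to spare.

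**Working it through.** **The plan's own figure.** There is none to reproduce. The documents state no power, SD, effect size or dropout for these endpoints. For context, a two-sample t-test with 20 vs 10 at two-sided 5% reaches 80% power only for a difference of 1.12 SD.

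**Inputs from the documents.** 20 vs 10 women (synopsis); linear regression of change (Section 15.4).

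**Assumed inputs.** Baseline and follow-up are lognormal with log-SD s of 0.5 to 0.9 and correlation r of 0.5 to 0.7 on the log scale. The effect is a constant ratio. There is no dropout, and tests are two-sided at 5%. Each setting used 20,000 or 40,000 simulated trials, so the standard error of a simulated power is at most √(0.25/20,000) = 0.0035.

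**Log scale by formula**, for s = 0.7, r = 0.7 and a 40% reduction (ln 0.6 = −0.511):
- Allocation factor: √(1/20 + 1/10) = 0.387.
- Log change: SD = s√(2(1 − r)) = 0.7 × √0.6 = 0.542; SE = 0.542 × 0.387 = 0.210; effect/SE = 0.511/0.210 = 2.43. The noncentral t with 28 degrees of freedom gives power 0.65.
- Log ANCOVA (log follow-up on arm and log baseline): residual SD = s√(1 − r²) = 0.7 × √0.51 = 0.500; SE about 0.500 × 0.387 = 0.194, before a small allowance for chance baseline imbalance; effect/SE about 2.64. Simulated power is 0.70.
- The variance ratio of log ANCOVA to log change is (1 − r²)/(2(1 − r)) = (1 + r)/2. This is 0.75 at r = 0.5 and 0.85 at r = 0.7.

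**Simulated power, 20 vs 10:**

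| log-SD | r | Reduction | Untransformed change | Log change | Log ANCOVA |
|---|---|---|---|---|---|
| 0.5 | 0.5 | 40% | 0.54 | 0.72 | 0.82 |
| 0.7 | 0.7 | 40% | 0.41 | 0.65 | 0.70 |
| 0.9 | 0.7 | 40% | 0.24 | 0.45 | 0.49 |
| 0.7 | 0.7 | 30% | 0.25 | 0.38 | 0.41 |

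With milder skew (log-SD 0.3, 20% reduction), power rises from 59% for untransformed change to 72% for log ANCOVA. Over a wider grid the loss runs from near zero, where power is already very high or very low, to about 44 percentage points.

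**Scale and baseline both contribute.** At log-SD 0.5, r = 0.7 and a 30% reduction, power is 48% for untransformed change, 63% for log change, 64% for untransformed ANCOVA and 68% for log ANCOVA.

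**Validity of untransformed change.** Type I error is 4.3% to 5.1%. Coverage of the 95% interval is 93.3% to 95.7% under no effect or a reduction, and up to 96.9% under an increase. If individual responses vary (SD 0.4 on the log scale), coverage is 95.4% to 97.2%. With 15 vs 15 it is 94.8% to 95.9%, so the 2:1 allocation moves coverage by only 1 to 2 points. It costs little power either: 48% against 51% at log-SD 0.5, r = 0.7 and a 30% reduction.

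**Validity of the alternatives.** Log ANCOVA keeps coverage of about 95% under a constant ratio effect. Untransformed ANCOVA does not: when there is a reduction, its coverage falls to between 84% and 94%. Adding the baseline without changing the scale is therefore not enough for skewed markers.

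**Additive effect.** A constant ratio effect favours logs, so the reverse was tried: a constant subtraction of 0.6 from a lognormal variable shifted up by 1, with r = 0.7. Power at log-SD 0.5, 0.7 and 0.9 was 0.86, 0.49 and 0.25 for untransformed change, against 0.97, 0.79 and 0.58 for log ANCOVA.

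**The case against.** Four points can be made for the plan.

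- **The text does not fix the original scale.** It never says untransformed or common variance, it carries the qualifier that the model is used where fitting, and regression of log change is also linear regression of change. This stands. The defect is an omission, not a wrong method that the plan commits to.
- **A SAP is to follow.** That is the natural place for such detail, but the promise is only that it will precede the final analysis. A scale chosen after data are seen would add to the freedom already present in imbalance-driven adjustment (synopsis) and three analysis approaches (Section 15.1).
- **Skew and effect sizes come from outside the documents.** This stands, and the figures above are conditional on it. The ordering of methods did not depend on a ratio effect, since the log scale was no worse in the additive check.
- **The trial disclaims power, and feasibility is primary.** This stands and limits the importance. It does not remove the claim to reasonable precision in Section 15.6.

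A reader might also infer that skew with 2:1 allocation makes the intervals wrong. The documents do not support this. A pooled-variance 5% test does have true error of 8.6% or 11.4% if the placebo SD is 1.5 or 2 times the active SD, and 2.8% if the active SD is 1.5 times the placebo SD. Those ratios are imposed, and nothing in the documents suggests them. Under the lognormal settings with a 30% to 40% reduction, the placebo/active SD ratio of untransformed change is only 1.09 to 1.17, and exactly 1 with no effect.

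**Conclusion.** The point holds as a loss of efficiency from an unspecified scale and a missing baseline covariate. If the markers are lognormal with log-SD 0.5 to 0.9 and correlation 0.5 to 0.7, and all women are followed up, analysing untransformed change gives up roughly 25 to 29 percentage points of power for a 40% reduction against log ANCOVA (0.82 − 0.54 = 0.28; 0.70 − 0.41 = 0.29; 0.49 − 0.24 = 0.25). It gives up about 16 points for a 30% reduction at log-SD 0.7 (0.41 − 0.25). The loss shrinks with milder skew.

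Type I error and coverage stay close to nominal, so the planned analysis would be valid but blunt. The feasibility rates in Section 15.3 are untouched, and so is the ordinal analysis of the NAFLD Activity Score. This is a cheap improvement to the exploratory comparisons, not a flaw that threatens the trial's main conclusion.

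**What to change.** In Section 15.4, or in the SAP before any unblinded outcome data are seen:

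1. List the positive, right-skewed markers: HOMA-IR, insulin, triglycerides, ALT, AST, MRI-PDFF and the sex hormones. For each, regress the log follow-up value on arm with the log baseline value as covariate, and report the between-arm ratio of geometric means with its 95% confidence interval. State how values at or below an assay limit are handled before taking logs.
2. For roughly symmetric measures such as LDL and weight, keep the original scale and add the baseline value as covariate.
3. Optionally, name an unequal-variance or robust interval as a sensitivity analysis.

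The cost is wording: no extra women, visits or assays. Effects on the logged markers are reported as percentage rather than unit differences, and one residual degree of freedom goes to the baseline (30 − 3 = 27 instead of 30 − 2 = 28).

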PLANNED INTERIM ANALYSES	The Data Safety Monitoring Board (DSMB) will review the progress of the study and perform an interim review of the safety data after the first 10 participants have completed 3 months of spironolactone, or at any time that a comprehensive review of safety is felt to be necessary. The committee will provide recommendations to [name] whether the nature, frequency, and severity of adverse effects associated with study treatment warrant the early termination of the study in the best interests of the participants, whether the study should continue as planned, or the study should continue with modifications. The DSMB may also provide recommendations as needed regarding study design, or changes to study conduct.
STATISTICS Primary Analysis Plan	The focus of the pilot trial will be feasibility testing and obtaining preliminary assessments of the effects of spironolactone. Exact 95% confidence intervals for rates of agreement to participate, meeting eligibility criteria, completing follow-up will be calculated using the binomial distribution. Between-group analyses will be performed according to the intention-to-treat principle. We will attempt to collect complete follow-up data on every randomized participant, regardless of adherence to treatment. As randomization in this small sample may not result in the perfect balance of relevant biological variables (e.g., age or weight between groups) we will perform analyses adjusting for any of these that are substantially imbalanced. A planned interim analysis will be conducted after the first 10 participants (25%) have completed 3 months of spironolactone. Interim results will provide useful preliminary safety and feasibility data.
Rationale for Number of Subjects	The sample size of 30 was determined based on budget and feasibility within a 4-year grant timeline. The sample size is also reasonable for pilot trial, and will allow us to estimate effects and feasibility with reasonable precision.

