### 8.2 Blinding

Due to the objectives of the study, the identity of test and control treatments will not be known to investigators, research staff, or patients. The following study procedures will be in place to ensure double-blind administration of study treatments

Access to the randomization code will be strictly controlled.

A color and size-matched placebo capsule that looks identical to the spironolactone capsule will be used.

Packaging and labeling of test and control treatments will be identical to maintain the blind.

No active drug measurements will be obtained.

The study blind will be broken on completion of the clinical study, after all study endpoints have been ascertained by blinded study coordinators and after the study database has been locked. At that time, the investigators, research staff, and participants will be informed about their treatment group assignments.

During the study, the blind may be broken **only** in emergencies when knowledge of the patient's treatment group is necessary for further patient management. Spironolactone has a longstanding favorable side effect profile. Therefore the only condition that will definitively lead to participant unblinding is pregnancy. The UCSF investigational pharmacy would then be notified and responsible for unblinding.

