## **9.2 Clinical Laboratory Measurements**

### **9.2.1 Blood Chemistry Profile**

Blood will be obtained and sent to the site's clinical chemistry lab for determination of serum sodium, potassium, creatinine at in person study visits. Liver tests (aspartate aminotransferase (AST/SGOT), alanine aminotransferase (ALT/SGPT), alkaline phosphatase, total bilirubin, and direct bilirubin), hemoglobin A1c, glucose, insulin, and lipid panel will be performed at each visit.

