### **12 DISCONTINUATION AND REPLACEMENT OF SUBJECTS**

#### **12.1 Early Discontinuation of Study Drug**

A subject may be discontinued from study treatment at any time if the subject, the investigator, or the Sponsor feels that it is not in the subject's best interest to continue. The following is a list of possible reasons for study treatment discontinuation:

- Subject withdrawal of consent (or assent)
- Subject is not compliant with study procedures
- Protocol violation requiring discontinuation of study treatment
- Adverse event that in the opinion of the investigator would be in the best interest of the subject to discontinue study treatment
- Lost to follow-up
- Positive pregnancy test

If a subject is withdrawn from treatment due to an adverse event, the subject will be followed and treated by the Investigator until the abnormal parameter or symptom has resolved or stabilized.

All subjects who discontinue study treatment should come in for End of Treatment visit as soon as possible and be encouraged to complete all visit procedures.

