## **15 STATISTICAL METHODS AND CONSIDERATIONS**

Prior to the analysis of the final study data, a detailed Statistical Analysis Plan (SAP) will be written describing all analyses that will be performed. The SAP will contain any modifications to the analysis plan described below.

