### **15.2 Demographic and Baseline Characteristics**

The following demographic variables at screening will be summarized by treatment group: race, ethnicity, age, body mass index, HOMA-IR, lipid levels, androgen levels, PCOS diagnosis, and menopausal status.

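### Section 15.4 fixes neither the outcome's baseline value as a covariate nor the analysis visit; a baseline-adjusted Month 6 model would close both gaps at small cost

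*Combined protocol and SAP*

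**What the plan says.** Section 15.4 prescribes logistic regression for dichotomous outcomes and, for the rest, ordinal logistic regression or "linear regression used to evaluate the association of spironolactone with change in either ordered categories or continuous measures". It mentions no covariate and no visit.

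The one covariate rule is in the synopsis (Primary Analysis Plan). It notes that a small randomized sample may be unbalanced, gives age and weight as examples, and says "we will perform analyses adjusting for any of these that are substantially imbalanced". It sets no cut-off, does not mention the outcome's own baseline, and does not say whether the adjusted model replaces the unadjusted one or accompanies it. The same paragraph commits to intention to treat and adds: "We will attempt to collect complete follow-up data on every randomized participant, regardless of adherence to treatment". Section 15.1 also calls for per-protocol and as-treated analyses of secondary outcomes, shown separately.

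Detail is deferred in Section 15: "Prior to the analysis of the final study data, a detailed Statistical Analysis Plan (SAP) will be written". Under Section 8.2 the blind is broken at study completion, "after all study endpoints have been ascertained by blinded study coordinators and after the study database has been locked".

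On timing, Appendix 1 labels both Month 6 and the optional Month 12 visit as end of study and treatment. Section 12.1 adds: "All subjects who discontinue study treatment should come in for End of Treatment visit as soon as possible".

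**The concern.** With 20 women against 10, the width of the intervals limits what the estimates can say about the biological signal that the synopsis hopes will support a larger trial. Two things are left open.

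- **Covariates.** A rule triggered by observed imbalance lets the data choose the model. Without a cut-off, two analysts could report different models from the same data. The variable most likely to predict the Month 6 value, the same measure before treatment, is not named.
- **Visit.** An end-of-treatment value could come from before Month 6 (early stoppers), from Month 6, or from Month 12 (extenders). A change score built on such a mixture would not estimate the effect of any one treatment duration.

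At stake is a cleaner estimate for secondary endpoints. The primary analysis, exact binomial intervals for feasibility rates (Section 15.3), is not affected.

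**Working it through.** **The plan's own figure.** The sample size is 20 + 10 = 30, which agrees with the 2:1 ratio. Section 15.6 bases it on budget and feasibility, so there is no power calculation to reproduce.

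**Inputs.** n = 30 (20:10) is from the synopsis. The documents do not give rho (correlation of baseline with follow-up), k (follow-up SD divided by baseline SD) or the fraction without a Month 6 value. All three are assumed below. A common slope and a common residual variance in the two arms are also assumed.

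**Cost of the covariate.** Residual degrees of freedom go from 28 to 27. With a normally distributed baseline, estimating the slope multiplies the expected variance by 1 + 1/(n − 4):

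- n = 30: 27/26 = 1.038
- n = 24 (16:8, if 20% lack a Month 6 value): 21/20 = 1.050

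Simulation of this term at 20:10 gave 3.84% (normal baseline), 3.87% (uniform), and 3.83% and 3.79% (two lognormal shapes).

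**Comparison with an unadjusted change score.** The ratio of expected variances, adjusted over change-only, is

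[(1 − rho²)k² / (1 + k² − 2·rho·k)] × (n − 3)/(n − 4).

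The denominator of the bracket minus its numerator is (1 − rho·k)², which is never negative. The bracket is therefore at most 1, and 27/26 is the ceiling at n = 30.

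| k | rho 0.5 | rho 0.7 | rho 0.8 | rho 0.9 |
|---|---|---|---|---|
| 0.8 | 0.593 | 0.652 | 0.665 | 0.631 |
| 1.0 | 0.779 | 0.883 | 0.935 | 0.987 |
| 1.1 | 0.849 | 0.956 | 1.005 | 1.038 |
| 1.2 | 0.904 | 1.003 | 1.035 | 1.015 |
| 1.3 | 0.947 | 1.029 | 1.036 | 0.953 |

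For k = 1 the bracket reduces to (1 + rho)/2, so break-even is rho = 2 × 26/27 − 1 = 0.926. For k = 1.2 the ratio first reaches 1 at rho = 0.692. For k = 0.8 it never does.

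**Interval width.** Mean 95% CI half-widths in baseline SDs, 20:10, from 20,000 simulated trials per setting, change-only to adjusted:

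- k = 1.0: 0.786 to 0.694 (12% narrower) at rho 0.5; 0.610 to 0.573 (6% narrower) at 0.7; 0.352 to 0.350 (under 1% narrower) at 0.9.
- k = 1.2: 0.875 to 0.832 (5% narrower) at rho 0.5; 0.688 to 0.689 (level) at 0.7; 0.567 to 0.578 (2% wider) at 0.8; 0.415 to 0.419 (1% wider) at 0.9.
- k = 0.8: 0.721 to 0.556 (23% narrower) at rho 0.5; 0.567 to 0.458 (19% narrower) at 0.7; 0.351 to 0.280 (20% narrower) at 0.9.

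**Cost of further covariates.** Baseline plus two non-prognostic variables gives 27/24 = 1.125, which is 1.125/1.038 = 1.083 times the variance with baseline alone.

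**Availability of data.** Appendix 1 schedules laboratory tests, hormones and MRI at Month 6 for everyone, including extenders. It puts the pre-treatment blood draws at Screening and the MRI at Day 1.

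**The case against.** The strongest reply is that this is a detail of exploratory endpoints in a trial the synopsis calls unpowered, and that a detailed SAP is promised. That stands as a limit on severity. It does not settle the point: the SAP's only deadline is before the final analysis, and Section 8.2 breaks the blind at study completion after database lock. A SAP written after unblinding would satisfy both sections.

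The gain in precision can also be questioned, and here the objection largely holds. In 7 of the 20 settings tabulated the adjusted model has slightly larger variance, the reductions of around 20% in interval width need k = 0.8, and the comparator is only one reading of Section 15.4. The case rests mainly on prespecification.

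A reader might infer more than the documents support:

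- *That baseline adjustment is ruled out.* Section 15.4 is silent on it.
- *That early, Month 6 and Month 12 values will be pooled, or the SAP written after unblinding.* The wording permits both, but neither is planned. Sections 9.2.3 and 9.4 list Month 6 and Month 12 as separate assessments.
- *That baseline is undefined.* Section 9.2.1 says "hemoglobin A1c, glucose, insulin, and lipid panel will be performed at each visit" and Section 9.2.3 places hormones at baseline, while Section 10.2 and Appendix 1 show no Day 1 draw. But Section 15.2, on baseline characteristics, says "The following demographic variables at screening will be summarized by treatment group" and lists HOMA-IR, lipids and androgens, and Appendix 1 agrees. What remains is loose wording.

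Two further limits stand. Women with a Month 6 value form a complete-case set, so a rule for missing values is still needed. Replacement of subjects (Sections 8.4 and 12.3, against 8.1) could also make the number randomized differ from 30; the ceiling falls as n rises.

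**Conclusion.** The point holds as a low-severity improvement. Section 15.4 leaves the baseline covariate and the visit open, and the only covariate rule depends on the observed balance. A prespecified Month 6 model costs one degree of freedom and at most 3.8% in expected variance at n = 30 (5.0% at n = 24), given a common slope and residual variance. Against an unadjusted change score with equal SDs, the benefit runs from about 12% narrower intervals at rho 0.5 to almost nothing at rho 0.9. The worst expected case is about 2% wider. If the analysts would have adjusted for baseline anyway, only the prespecification is gained.

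It would be wrong to conclude that the trial's feasibility result is at risk or that adjustment must tighten every estimate.

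**What to change.** In Section 15.4, and in a SAP finalised before unblinding, for continuous laboratory, hormone and MRI measures:

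1. Fit the Month 6 value (or change to Month 6) on treatment plus the measure's pre-treatment value: the Screening draw for laboratory tests and hormones, the Day 1 scan for MRI.
2. Make this the intention-to-treat analysis, in all randomized women with a Month 6 value, extenders included and whatever their adherence. Keep the per-protocol and as-treated analyses of Section 15.1 as separate presentations.
3. Report Month 12 separately and do not pool last available values. State a Month 6 window and how early end-of-treatment values and missing Month 6 values are handled; early values could enter one sensitivity analysis.
4. Use this model in place of the imbalance trigger. Adjustment for age and weight can be at most one prespecified sensitivity analysis.
5. Keep biopsy measures exploratory and report the biopsy month, because the end-of-treatment biopsy is optional (Section 9.3) and moves to Month 12 for extenders (Section 10.6).

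Two sets of passages also need reconciling. Radiologic endpoints are secondary in the synopsis but sit under primary endpoints in Section 5.1, so it is unclear whether Section 15.4 governs MRI. Placebo duration differs between the synopsis study-design row, the synopsis control-product row and Section 4.1, which decides whether Month 12 has a concurrent control.

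The cost is wording in Section 15.4, the synopsis and the SAP, one degree of freedom, and a written rule for early and missing values. No new visit or procedure is needed.
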